5.11.3.2. Key Secondary Efficacy Analyses

For PFS, the same analyses used for the analyses of the primary endpoint OS will be performed. In addition, as sensitivity analyses, the primary PFS analysis will be repeated using different PFS censoring rule as defined in [Table JGDJ.5.2](#), to evaluate whether and to what extent the conclusion of the PFS analysis under the primary definition would be affected under the different censoring rules.

This comparison of PFS using the same method as that for the primary analysis of PFS will be considered inferential only in case of significant results for OS analysis (that is, as a gatekept analysis so as not to inflate the overall type I error rate).

The main PFS analysis will also be repeated for a subset of patients started monotherapy.

If PFS analysis is significant, then testing on ORR will be conducted. Objective tumor response (CR+PR) rate (ORR) will be reported along with exact confidence bounds (CI: 95%) and compared using the Cochran-Mantel-Haenszel test adjusting for the stratification variables. A sensitivity sensitivity analysis on ORR will be performed to consider only confirmed response (using 4-week interval for confirmation).

5.11.3.3. Analyses of Other Secondary Efficacy Variables

All time-to-event variables (including those defined in Sections [5.2.1.1](#) and [5.2.1.3](#)) will be analyzed using stratified log-rank tests (analogous to the primary analysis) for comparisons between study arms, stratified Cox models (for between-arm statistics including the treatment HR), and Kaplan-Meier method (for within-arm statistics).

Disease control (CR+PR+SD) rate will be reported along with exact confidence bounds (CI: 95%) and compared using the Cochran-Mantel-Haenszel test adjusting for the stratification variables.

Patient listings of tumor assessments (target and non-target lesion assessments and tumor response), OS, and PFS will be provided.

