5.1. Sample Size

The primary objective of this trial is to compare doxorubicin plus olaratumab versus doxorubicin plus placebo with respect to OS in 2 populations:

- (1) Patients with advanced or metastatic STS not amenable to treatment with surgery or radiotherapy with curative intent
- (2) Patients with advanced or metastatic LMS not amenable to treatment with surgery or radiotherapy with curative intent

Population (1) will be analyzed for efficacy among all randomized study patients (the intent-to-treat [ITT] population). Population (2) will be analyzed as the subset of randomized patients with LMS. Therefore, this document will consider Population (1) as synonymous with the ITT study population, and refer to Population (2) as the “LMS population”. The study will be considered a positive study if either the ITT or LMS populations (or both) show a statistically significant improvement in OS with the regimen of doxorubicin plus olaratumab.

The study will enroll 460 patients in 1:1 randomization (230 patients in the investigational arm and 230 patients in the control arm). Enrollment will be conducted so that approximately 200 patients with LMS and 260 patients with other (non-LMS) histology will be randomized. The final analysis will occur only when both a minimum of 131 OS events have been observed in randomized patients with LMS and a minimum of 322 OS events have been observed in randomized patients overall.

See Section 5.11.1 for a detailed description of the statistical testing plan according to the graphical approach of Maurer and Bretz (2013).

The overall type I error rate for the study is controlled at 0.025 (1-sided). The associated sample sizes for the hypotheses that form the primary objective are based on the initial allocation of alpha (OS ITT $\alpha = 0.02$ and LMS $\alpha = 0.005$, 1-sided). One interim efficacy analysis will be performed at 194 ITT OS events.

If the ITT OS hazard ratio (HR) is assumed to be 0.723, and assuming 322 ITT OS events, a log-rank comparison of OS between study arms in the ITT population will have 80% power at the nominal alpha of 0.02. Assuming 30% censoring, a total sample size of 460 randomized patients is required.

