Time to any progression based solely on increased sum of target lesions is defined as the time from the date of randomization to the first date of radiologic disease progression based solely on an increased sum of target lesions. Time to progression based on an increased sum of

target lesions will be censored at the first date of radiologic disease progression if that progression was based solely on new lesions. If there is no radiologic disease progression, time to any progression based on an increased sum of target lesions will be censored following the rules of [Table JGDJ.5.1](#), with the exception that censoring will be applied at the date of death (if no previous event or censoring).

Objective response rate (ORR) is defined as the proportion of randomized patients achieving a best overall response of PR or CR per RECIST v.1.1. Patients who do not have any postbaseline tumor response assessments are considered non-responders and are included in the denominator when calculating the response rate. Tumor assessments performed after initiation of new anticancer treatment (systemic therapy) will be excluded from evaluating the best overall response.

Disease control rate (DCR) is defined as portion of randomized patients achieving a best overall response of CR, PR, or SD per RECIST v.1.1. Patients who do not have any postbaseline tumor response assessments for any reason are considered non-responders and are included in the denominator when calculating the response rate. Tumor assessments performed after initiation of new anticancer treatment (systemic therapy) will be excluded from evaluating the best overall response.

Duration of response (DoR) is defined for each patient with a best response of CR or PR as the duration from the first date of CR or PR to the first date of radiologic disease progression or death due to any cause. DoR will be censored according to the same rules as PFS.

Duration of Disease Control (DDC) is defined for each patient with a best response of CR, PR, or SD as the time from randomization to the first date of radiologic disease progression or death due to any cause. DDC will be censored according to the same rules as PFS.

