Figure JGDJ.5.2. Graphical representation of testing sequence conditional on rejection of either H_{11} or H_{12} to illustrate updating of alphas at each node and weight at each edge.

Assigning $\epsilon=0.001$ initially focuses virtually all the alpha on the primary endpoints. The iterative process of subsequent updating of the graph and redistribution of α is described in [Table JGDJ.5.5](#) below and is repeated until no further hypotheses can be rejected.

Table JGDJ.5.5. Planned Alpha Spending Using Graphical Approach

Test	Node α at Analysis
1. Initial Graph (Figure JGDJ.5.1)	
LMS OS	0.005
ITT OS	0.02
2. Graph when H_{11} LMS OS is rejected (Figure JGDJ.5.2; left)	
ITT OS	0.025
2.1 PFS* (If ITT OS is further rejected)	0.025
2.1.1 ORR** (If PFS is further rejected)	0.025
3. Graph when H_{12} ITT OS is rejected (Figure JGDJ.5.2; right)	
LMS OS	0.02498
3.1 PFS* (if LMS OS is further rejected)	0.025
3.1.1 ORR** (if PFS is further rejected)	0.025
3.2. PFS* (if LMS OS is not rejected)	0.00002
3.2.1 ORR** (if PFS is further rejected)	0.00002

Abbreviations: ITT = intent-to-treat; LMS = leiomyosarcoma; ORR = objective response rate; OS = overall survival; PFS = progression-free survival.

* Information fraction for PFS events at 60% OS events interim is 82% based on design assumptions that PFS median for control arm is 4.5 months, and experimental arm is 7.15 months.

** Information fraction for ORR response at 60% OS events interim is 85% based on design assumptions that ORR in response time is 6 months for both arms, and response rate for control arm is 12% and for experimental arm is 19%.

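### Duration of response and duration of disease control get between-arm log-rank tests and hazard ratios in subsets chosen after randomization; for duration of response the stratified test is also sparse

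*SAP*

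**What the plan says.** SAP 5.11.3.3 sets one rule. It covers "All time-to-event variables (including those defined in Sections" 5.2.1.1 and 5.2.1.3, and these variables "will be analyzed using stratified log-rank tests (analogous to the primary analysis) for comparisons between study arms". Stratified Cox models supply the treatment hazard ratio, and Kaplan-Meier the within-arm statistics.

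Two variables in SAP 5.2.1.1 exist only for some randomized patients:

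- DoR "is defined for each patient with a best response of CR or PR as the duration from the first date of CR or PR", ending at radiologic progression or death.
- DDC "is defined for each patient with a best response of CR, PR, or SD as the time from randomization" to the same events.

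Both are censored like PFS. SAP 4.2 and Protocol 6.2 list both among the secondary objectives to be compared between arms. SAP 5.3 stratifies every efficacy analysis by prior systemic therapies, histology and ECOG status. SAP 5.2 sets two-sided 0.05 as the default test level, and SAP 5.6 leaves everything except OS, PFS and ORR without multiplicity control. Neither document calls the DoR or DDC comparison descriptive or notes how its analysis set is selected.

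**The concern.** A log-rank test of OS or PFS compares groups formed by randomization. A log-rank test of DoR compares patients who responded on olaratumab with patients who responded on placebo. If treatment changes who responds, those groups differ in kind, and their hazard ratio mixes the effect on duration with the difference in membership. The plan expects such a change: the notes to SAP Table JGDJ.5.5 assume that the "response rate for control arm is 12% and for experimental arm is 19" per cent.

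DDC has the same problem in another form. Its clock starts at randomization, but Protocol Attachment 6 requires stable disease to be seen at least 5 weeks after randomization. DDC is therefore close to PFS with the early progressors removed, and the number removed may differ by arm.

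At stake are a nominal p-value and hazard ratio for two listed secondary objectives, which would be read as randomized comparisons. For DoR there is a smaller, separate issue: few responders spread over many strata.

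**Working it through.** **Inputs.** 230 patients per arm (SAP 5.1); response rates 12% and 19% (SAP Table JGDJ.5.5, notes); 2 × 4 × 2 = 16 analysis strata (SAP 5.3; Protocol 12.2.6 gives the same count). The plan states no sample size or power for DoR or DDC. Its own size reproduces: 322 OS events / 0.70 = 460 patients, and 322 events at HR 0.723 and one-sided 0.02 give 80.4% power (Schoenfeld).

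**Expected DoR set.** Control 0.12 × 230 = 27.6; olaratumab 0.19 × 230 = 43.7; total 71.3. Per stratum 71.3 / 16 = 4.5 (1.7 control, 2.7 olaratumab).

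**Selection, illustrated for DoR.** Assumptions, none from the documents:

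- Every patient who would respond on control also responds on olaratumab, for the same time.
- A further 7% respond only on olaratumab, with mean duration k times that of the others.
- Durations are exponential, with mean 1 in control responders.

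Among responders, control survival is S_C(t) = exp(−t). Olaratumab survival is S_T(t) = (12/19)exp(−t) + (7/19)exp(−t/k). The Cox hazard ratio is the large-sample solution for responders in the ratio 27.6 to 43.7. Mean time in response per randomized patient is 0.12 on control and 0.12 + 0.07k on olaratumab.

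| k | HR among CR/PR patients, no censoring | Same, 20% of control durations censored | Mean time in response per randomized patient, olaratumab / control |
|---|---|---|---|
| 0.5 | 1.22 | 1.24 | 0.155 / 0.12 = 1.29 |
| 0.67 | 1.14 | 1.14 | 0.167 / 0.12 = 1.39 |
| 0.8 | 1.08 | 1.08 | 0.176 / 0.12 = 1.47 |

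No patient's response is shortened, and time in response per randomized patient rises by 29% to 47%. The hazard ratio among responders still points against olaratumab.

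**Sparse strata, DoR.** The documents give no stratum distribution beyond about 200 LMS patients in 460. Three distributions were simulated, with an assumed 20% censoring. Prior-therapy and ECOG splits were 50/50 and 50/50 (even), 70/30 and 60/40 (middle), and 80/20 and 65/35 (skewed).

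| Assumed distribution | Empty strata | Strata with fewer than 5 responders | Strata with both arms | Informative events / all events | Information kept |
|---|---|---|---|---|---|
| Even | 0.4 | 9.4 | 11.4 | 34 / 57 | 59% |
| Middle | 1.2 | 9.8 | 10.2 | 36 / 57 | 62% |
| Skewed | 2.3 | 10.4 | 8.9 | 38 / 57 | 65% |

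Information kept is the stratified log-rank variance divided by the unstratified variance.

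**The same check for DDC.** The documents give no disease control rate. At an assumed 40% to 80%, 184 to 368 patients enter, or 11.5 to 23 per stratum. At 50% to 70%, about 14 to 16 strata contain both arms and 81% to 86% of the information is kept.

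**LMS population.** Protocol 12.2.1.1 repeats efficacy analyses there. Assuming 100 patients per arm and the same response rates, 12 + 19 = 31 responders fall in 4 strata, about 7.8 each.

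**The case against.** Several points on the other side stand.

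- **Consequences are limited.** DoR and DDC lie outside the testing graph. They cannot make the study positive and open no further test.
- **Sparse strata do not bias the log-rank test.** They cost power. SAP 5.3 already permits non-stratified sensitivity analyses of any efficacy variable, though it does not require them.
- **Valid comparisons already exist nearby.** ORR and DCR use all randomized patients as denominator. SAP 5.11.3.2 gives PFS the same analyses as OS, which under 5.11.2 include a restricted mean difference with its confidence interval. Since DDC shares the start, events and censoring of PFS, an all-randomized version of DDC would largely duplicate that result.
- **The illustration is one scenario.** Other selection patterns could flatter olaratumab.

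A reader might infer more than the documents support. Both durations are not restricted to responders: DDC includes stable disease. The strata are not almost empty: for DoR they are sparse, with about 0 to 2 of 16 empty, and DDC does not share the problem at the rates examined.

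None of this makes the planned DoR and DDC comparisons randomized. An unstratified sensitivity analysis would remove the loss of information but not the selection.

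**Conclusion.** The concern holds for both endpoints as a matter of selection: a between-arm test and hazard ratio are planned in sets defined by a post-randomization outcome, with no statement that they are descriptive. It weighs more for DoR, where the design itself assumes different response rates. The possible distortion is a hazard ratio of about 1.08 to 1.22 with no response shortened; this rests on exponential durations, no censoring and extra responders lasting 0.8 to 0.5 times as long. It shows that the sign can mislead and does not predict the direction in this trial.

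The loss of information, to roughly 59% to 65% of the unstratified test, applies to DoR only and rests on assumed stratum splits and censoring. It is a matter of power. Because neither endpoint is alpha-controlled, the change is desirable and not essential.

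**What to change.** Except DoR and DDC from the between-arm sentence in SAP 5.11.3.3. Report each by Kaplan-Meier within arm (median and 95% CI), with no between-arm p-value or hazard ratio, and state that the analysis sets are selected by outcome.

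If DoR is to be compared, prespecify restricted mean time in response over all randomized patients, with non-responders counted as zero and a stated time horizon. For DDC, refer to the planned PFS comparison, including its restricted mean difference, and to the DCR comparison; no new analysis is needed.

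The cost is a change of SAP wording and, if the DoR comparison is wanted, one more programmed analysis. What is lost is a p-value among CR/PR or CR/PR/SD patients.

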PD on study therapy	Situation			Event / Censor	Date of Event or Censor
	PD after end of study therapy but prior to next line of treatment	PD on next line of treatment	Death		
Yes	No	Yes	Yes / No	Event	Event at PD date on next line of treatment
Yes	No	No	No	Censored	Censoring at the date PD-free on next line of treatment
Yes	No	No	Yes	1) Event 2) Censored	Event at death date if no further treatment, otherwise censoring at the date PD-free on next line of treatment
No	Yes	Yes	Yes / No	Event	Event at PD date on next line of treatment
No	No	Yes	Yes / No	Censored	Censoring at start of next line of treatment
No	Yes / No	No	No	Censored	Censoring at the date PD-free on next line of treatment
No	Yes	No	Yes	1) Event 2) Censored	Event at death date if no further treatment, otherwise censoring at the date PD-free on next line of treatment
No	No	No	Yes	Censored	Censoring at start of next line of treatment

Time to any progression (censoring for death without progression) is defined identically to PFS, except that the time to any progression will be censored at the date of death if there is no prior or concurrent radiologic disease progression. Otherwise, censoring follows the rules described in [Table JGDJ.5.1](#).

Time to any new metastasis (censoring for death and/or for progressive disease (PD) due to increased sum of target lesions) is defined for each patient as the time from the date of randomization to the first date of radiographic documentation of 1 or more new lesions. Time to any new metastases will be censored at the first date of radiologic disease progression if that progression was based solely on an increased sum of target lesions (without new lesions). If there is no radiologic disease progression, time to any new metastases will be censored following the rules of [Table JGDJ.5.1](#), with the exception that censoring will be applied at the date of death (if no previous event or censoring).

New-metastases-free survival (nMFS) is defined for each patient as the time from the date of randomization to the first date of radiographic documentation of 1 or more new lesions, or to the date of death from any cause (whichever occurs first). nMFS will be censored at the first date of radiologic disease progression if that progression was based solely on an increased sum of target lesions (without new lesions). Otherwise, nMFS will be censored for analysis in a manner analogous to PFS (following the rules of [Table JGDJ.5.1](#)).

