5.11.2. Primary Efficacy Analyses

For the primary comparison of OS, the primary endpoint, between the assigned study treatment arms, a stratified log-rank test will be performed to test the following statistical hypotheses about the OS HR for olaratumab over placebo:

H_0 : OS HR ≥ 1.00 (Olaratumab not superior to placebo)

H_a : OS HR < 1.00 (Olaratumab superior to placebo)

The stratification will be based on IWRS data that used for randomization (see Section 5.3 for more details). An unstratified log-rank test will also be performed as sensitivity analysis.

The following analyses of OS will also be performed:

- Summary of OS events (number and percentage), censoring rate, and reasons for censoring
- Restricted mean difference in OS between the treatment groups and its 95% CI, with the area under the Kaplan-Meier survival curve calculated up to the minimum across treatment arms of the maximum observed (that is, event or censored) time
- Kaplan-Meier survival curve (Kaplan and Meier, 1958) by treatment group will be provided.
- The Kaplan-Meier method will be used to estimate parameters (medians, quartiles, and percentages), difference of percentage and associated 95% CI and p-values for time-to-event analyses on each treatment group at 3, 6, 9, 12, and 24 months. Patients who did not have the event at the corresponding time point will be considered right-censored observations.
- HR for treatment effect will be estimated using Cox proportional hazards (PH) model stratified identically to the primary log-rank test with assigned treatment as the only covariate, reported with 2-tailed 95% CIs and Wald's test p-value. This Cox PH model will be referred to as the primary Cox PH model henceforth.

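### Kaplan-Meier summaries of time to new metastasis, target-lesion progression and any progression censor competing events, so they overstate first-event incidence and can distort the absolute difference between arms

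*SAP*

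**What the plan says.** SAP 5.11.3.3 covers all time-to-event variables, including those defined in 5.2.1.1. Arms are compared with stratified log-rank tests and "stratified Cox models (for between-arm statistics including the treatment HR"). Each arm is described by the "Kaplan-Meier method (for within-arm statistics").

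SAP 5.2.1.1 sets the censoring for three of these variables:

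- **Time to any new metastasis.** "Time to any new metastases will be censored at the first date of radiologic disease progression if that progression was based solely on" growth of the target lesions. Where there is no radiologic progression, the PFS censoring rules apply "with the exception that censoring will be applied at the date of death (if no previous event or censoring").
- **Time to target-lesion-only progression.** It "will be censored at the first date of radiologic disease progression if that progression was based solely on new lesions", and again at death.
- **Time to any progression.** Death without prior or concurrent radiologic progression is censored.

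Neither document names a cumulative incidence function or any other competing-risks method.

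**The concern.** Kaplan-Meier treats a censored patient as still able to have the event later, at the same rate as those still followed. A patient who has died cannot. A patient whose first progression is of the other type can no longer have the named event as a first event. With such patients censored, 1-KM describes a setting in which the competing event does not occur. It is not the share of trial patients observed to have the named event first.

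Readers will take the curves, medians and percentages as patient proportions. The excess depends on the competing hazard, which may differ between arms if the drug affects progression or death. The visual and numerical gap between arms can then be misleading as well as the level in each arm.

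**Working it through.** The documents give no numerical figure for these endpoints, so there is none to reproduce. The calculation starts from the SAP's PFS design assumption.

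**Inputs**

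- From the notes to SAP Table JGDJ.5.5: "PFS median for control arm is 4.5 months, and experimental arm is 7.15 months". With exponential times, h = ln 2 / median, which gives 0.1540 (control) and 0.0969 (experimental) per month; HR = 4.5/7.15 = 0.629.
- Assumed, because the documents do not give it: p, the share of first PFS events that are of the named type. Range 0.3 to 0.7.
- Assumed in the base case: the same HR on every cause, so p is equal in both arms.

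**Formulas**

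- 1-KM with competing events censored: 1 − exp(−p·h·t)
- Cumulative incidence as first event: p·(1 − exp(−h·t))

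**Base case, t = 12 months** (h·t = 1.848 control, 1.163 experimental)

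| p | 1-KM, control vs experimental | Difference | First-event incidence | Difference | Ratio of differences |
|---|---|---|---|---|---|
| 0.3 | 42.6% vs 29.5% | 13.1 | 25.3% vs 20.6% | 4.6 | 2.82 |
| 0.5 | 60.3% vs 44.1% | 16.2 | 42.1% vs 34.4% | 7.7 | 2.09 |
| 0.7 | 72.6% vs 55.7% | 16.9 | 59.0% vs 48.1% | 10.8 | 1.56 |

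A simulation of 400,000 patients per arm at p = 0.5 gave 60.4% vs 44.1% for 1-KM and 42.2% vs 34.4% for incidence. At p = 0.5 the ratio of differences is 1.21, 1.45, 1.74, 2.09 and 4.26 at 3, 6, 9, 12 and 24 months.

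**Coherence check.** Suppose first events split evenly between the two progression types. The two control-arm 1-KM values at 12 months then sum to 2 × 60.3% = 121%, although only 1 − exp(−1.848) = 84% of patients have had any PFS event. Kaplan-Meier would also give medians of ln 2/(0.5·h) = 9.0 and 14.3 months for something that at most half of patients ever have as a first event.

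**Changing where the effect falls**

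- All of the PFS effect on the named event (p = 0.4 to 0.7 in control, 3 to 24 months): the ratio is 1.05 to 1.92.
- All of the effect on the competing events (p = 0.5, 12 months): 1-KM is 60.3% in both arms, while first-event incidence is 42.1% in control and 54.6% in the experimental arm.

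**Time to any progression.** Only death competes here. If deaths are an assumed 10% of first events (p = 0.9), 12-month 1-KM is 81.1% vs 64.9% against an incidence of 75.8% vs 61.9%; the ratio of differences is 16.2/13.9 = 1.16. At 20% (p = 0.8) it is 77.2% vs 60.6% against 67.4% vs 55.0%, with ratio 16.6/12.4 = 1.34.

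The calculation ignores the 6-week scan interval. It also leaves out progression in non-target lesions, which the definitions in SAP 5.2.1.1 do not clearly assign.

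**The case against.** **The incidence figures have a narrow meaning.** Progression in target lesions does not prevent a later new lesion; it ends observation, because protocol 10.1.2 no longer requires scans after objective progression. So 42% vs 34% is the proportion whose first event is a new lesion. A reader might take it as the proportion who ever develop new metastases. The documents do not support that: the ever-proportion is at least as large and is not observed. If death alone is treated as terminal, with target-lesion progression as independent censoring, p = 0.5 and deaths an assumed 10% or 20% of first events, incidence is p/(p+d)·(1 − exp(−(p+d)·h·t)), where d is the death share. That gives 56% vs 42% or 52% vs 40% at 12 months, differences of 14.0 and 12.1 points. The ratio to the Kaplan-Meier difference falls to 1.16 or 1.35. This stands, and it is why the estimate needs a first-event label.

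**Doubling is not a general result.** A reader might infer that Kaplan-Meier doubles, or always inflates, the absolute difference. That rests on an assumed event mix, a later time point and one HR on every cause. The documents supply none of these.

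**Absolute differences are not clearly planned here.** SAP 5.11.2 lists Kaplan-Meier estimates with "difference of percentage and associated 95% CI and p-values for time-to-event analyses on each treatment group at 3, 6, 9, 12, and 24 months", but under OS, and 5.11.3.2 carries the OS analyses over to PFS. SAP 5.11.3.3 promises only within-arm statistics. This stands, although two curves on one plot invite the comparison.

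**The consequence is small.** The protocol lists these as additional efficacy measures (10.1.4), outside the set with type I error control (SAP 5.6). The censoring is disclosed, and the conditional lung-lesion analyses of time to new metastases use Cox models (SAP 5.11.5). This stands. New-metastases-free survival counts death as an event but still censors target-lesion-only progression, so it only partly fills the gap.

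**Conclusion.** The concern holds for descriptive reporting. Whenever competing events come before events of the named type, 1-KM overstates the proportion of patients whose first event is of that type. That is a mathematical property of the estimator; only its size needs assumptions. In the base case at 12 months with a 50% share, the overstatement is 60.3/42.1 = 1.43-fold in control and 44.1/34.4 = 1.28-fold in the experimental arm.

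The effect on the difference between arms has no fixed direction. Kaplan-Meier may exaggerate the difference or hide one, depending on which causes the treatment affects.

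A reader might also infer that the between-arm results are invalid. They are not: the stratified log-rank test and Cox HR remain valid comparisons of cause-specific hazards. No primary or key secondary conclusion is touched.

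**What to change.** In SAP 5.11.3.3, replace Kaplan-Meier for these three variables with the Aalen-Johansen cumulative incidence by arm:

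- For time to any new metastasis and time to target-lesion-only progression, treat death and the other type of progression as competing events.
- For time to any progression, treat death alone as the competing event.
- Label each estimate as the incidence of that type as first event.

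Keep the stratified log-rank test and stratified Cox model, and label their results cause-specific.

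The cost is a few lines of SAP text and a standard procedure, with no new data. The downside is that medians may not be reached. For an event that fewer than half of patients have first, that is the accurate result.
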